when answering the questions. For all follow-up research appointments, the directions will ask the subject to think about their coping strategies used since the last research appointment. Question/prompt items remain the same between the two versions.

- PROMIS is a well validated and widely used scale that measures the quality of social and occupational functioning.
- Social Connectedness Scale (SCS) (Lee and Robbins 1995; 1998) is a 20 item, 6-point scale, self-report assessing psychological belonging or interpersonal closeness with good reliability ($\alpha=.91$).
- Patient Health Questionnaire (PHQ) (Spitzer et al., 1999) was developed for use in primary health settings and screens for DSM psychiatric diagnosis of major depression and generalized anxiety at baseline.
- The Kessler 10 (K10) (Kessler et al., 2003) is a brief, 10-item self-report measure of general psychiatric distress will be collected at baseline and follow up points to address change in psychiatric symptoms over time. K10 has good reliability and is used in World Health Organization mental health surveys in 30 countries.
- HIV Risk from the Sexual Experiences and Risk Behavior Assessment Schedule (SERBAS): A summary item from the Sexual Experiences and Risk Behavior Assessment Schedule (SERBAS), used as primary outcome in large HIV risk reductions studies (Tross et al., 2010), elicits the number of episodes of occasions of vaginal or anal intercourse without a condom over the last 90 days using time-line follow back cues for recall.
- Time Line Follow-Back (see above) will query intravenous drug use, and episodes of sharing needles.
- Columbia Suicide Severity Rating Scale (C-SSRS) (Posner et al., 2008):_ The C-SSRS will be administered only to subjects who have endorsed suicidal ideation (SI) per the Patient Health Questionnaire (PHQ). There is one item on the PHQ that assesses self-reported SI using a Likert scale of 0-3 (0 = not at all; 3= nearly every day). A score of 1 or higher is considered an SI endorsement, which will warrant administration of the C-SSRS. Should the C-SSRS results indicate an SI presence/plan, a Hub PPI provider (physician or nurse practitioner) will take over the evaluating situation and follow PPI's SI policy.

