8.2 Sample size determination

Previous studies of MAT treatment of OUD indicate substantial drop out rates--typically in the 40% to 50% range still retained in treatment at 24 weeks. Assuming 40% retention in the TAU treatment group, a sample size of 100 patients per treatment group (total N = 200) is selected to ensure sufficient power of 80% with a two-sided level of significance of 5% to be able to detect a difference of at least 19.7% between the TAU vs reSET-O + TAU treatment groups (i.e., 40% retained in TAU vs 59.7% retained in reSET-O + TAU). This difference of 19.7% is equivalent to an odds-ratio of 2.22 and would be clinically meaningful.

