8.3 Statistical methods

Outcome Measures and Covariates

Primary outcome: The primary outcome will be a binary indicator of whether or not the patient is retained on MAT (methadone, buprenorphine, or buprenorphine-naloxone) treatment through 24 weeks. For those who drop out before 24 weeks, time (week) of dropout will be recorded, and they will be considered as not retained.

Secondary outcomes: 1) weeks of treatment retention (time to drop-out 0-24 weeks, survival; number of weeks retained, continuous); 2) urine-confirmed abstinence from opioids in the last 4 weeks (longitudinal (weeks 4, 8, 12, and 24), binary); 3) Days using opioids in the last 4 weeks (longitudinal, continuous); 4) Days using other drugs/alcohol in last 4 weeks (longitudinal, continuous); 5) coping strategies (CSS mean score; longitudinal, continuous); 6) social functioning (EuroQol, SCS, global scores and subscales; longitudinal, continuous); 6) overall mental health symptoms (K10; longitudinal, continuous); 7) HIV risk behavior—days in past 30 of vaginal or anal sex without a condom (longitudinal, continuous); Any needle sharing in past 4 weeks (longitudinal, binary); 7) Treatment satisfaction at week 24 (IAFF; continuous); 8) Serious adverse events (binary).

Additional variables: *Covariates, primary and secondary analyses:* Stratification factors: 1) any intravenous drug use (binary); 2) treatment with methadone vs buprenorphine at Hub vs buprenorphine at Spoke (categorical). *Moderators:* 1) both stratification factors will be explored as moderators; 2) demographic characteristics (gender, age, ethnicity etc.); 3) prescription opioid use only vs any heroin or fentanyl use (binary); 4) other substance use at baseline (any cannabis, any stimulant, any heavy drinking days; binary); 5) Probable major depression at baseline (binary based on PHQ score); 6) history of prior treatment for opioid use versus first treatment episode (binary). *Mediators:* 1) social functioning (EuroQol; continuous); 2) social connectedness (SCS; continuous); 3) opioid craving (continuous); 4) coping (CSS; continuous); and 5) mental health symptoms (K10; continuous).

Intent to Treat, Dropouts, and Missing Data

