Moderation Statistical Models: The effect of randomization to the reSET-O+TAU arm will be estimated for subpopulations based on the demographic and baseline characteristics selected as moderators (see above). We will estimate the moderation effect on primary outcome using a similar model to Aim 1 primary outcome with the inclusion of moderator by treatment interaction: $Y_i = \beta_0 + \beta_1 Trx_i + \beta_2 M_i + \beta_3 Trx_i M_i + \beta_4 C_i + s_i$ where M_i is the moderator status for i^{th} subject and Trx_i is subject's treatment assignment. Regardless of the significance of the interaction term, we will use the model to estimate the 95% confidence interval of the treatment effect for each level or category of the moderator variable. The moderator analyses are exploratory and hypothesis generating, but significant moderator effects can be useful in planning future efforts at implementation of reSET-O by identifying subgroups that may particularly benefit. Identifying subgroups where there is less benefit may suggest future modifications to reSET-O or its implementation strategy to achieve better effect in those subgroups.

Mediation Statistical Models: The effect of randomization to the reSET-O +TAU arm will be estimated when accounting for potential mediators (see above). In particular, we are interested in testing whether an impact of treatment on the primary outcome of 24 week buprenorphine retention is mediated by craving and by coping skills (CSS), which are targets of the therapy lessons or modules of reSET-O, as well as social functioning (PROMIS) and social connectedness. We will simultaneously estimate both the total effect of treatment assignment on primary outcome and the indirect of treatment assignment on primary outcome mediated through the intended target mediators using structural equation modeling (SEM) in software MPlus (Taylor, MacKinnon and Tein 2008). The indirect effect is estimated by the product of the effect of treatment assignment on the mediator and the effect of the mediator on the primary outcome while adjusting for treatment assignment. SEM will provide an estimate of the indirect effect of each mediator as well as its bootstrapped 95% confidence interval. These mediational analyses explore whether the effect of reSET-O on the primary outcome is being channeled through reSET-O

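### The mediation model specifies no baseline adjustment of the unrandomised mediator-to-retention path, so the indirect effect can be biased for any mediator that the app shifts

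*Combined protocol and SAP*

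**What the plan says.** Section 8.3 (Moderation and Mediation) estimates the indirect effect in a structural equation model as a product: the effect of assignment on the mediator, times "the effect of the mediator on the primary outcome while adjusting for treatment assignment". The interval is a bootstrapped 95% interval. No baseline score, stratification factor or other covariate is named for either path, and no sensitivity analysis for mediator-outcome confounding is planned. The moderation equation just before it does carry a covariate term.

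The mediators listed in section 8.3 are social functioning, social connectedness, and "opioid craving (continuous); 4) coping (CSS; continuous); and 5) mental health symptoms (K10; continuous". The list gives EuroQol as the social-functioning instrument, whereas the mediation paragraph gives PROMIS. Section 7.2.1 collects PROMIS, the connectedness scale, the coping scale and craving items at baseline. It says of the K10 that it "will be collected at baseline and follow up points to address change in psychiatric symptoms over time". Section 7.2.2 repeats the measures at weeks 4, 8, 12 and 24. EuroQol is not among the instruments described.

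Two further statements bear on the point. Section 8.3 has a general rule that covariates found to be related to outcome enter the hypothesis-testing models. Section 1.3 labels the mediation analysis exploratory.

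**The concern.** Randomisation protects the path from treatment to mediator. It does not protect the path from mediator to retention, because patients are not randomised to their follow-up craving or coping. A patient who starts with less craving or better coping is likely to score better later and may also stay longer. Conditioning on arm does not remove that common cause, so the second path can be non-zero when the mediator does nothing.

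The product of paths carries this bias whenever the app also moves the mediator. That condition is not remote: section 8.3 describes craving and coping as what the app's lessons aim at. If the mediator does affect retention, confounding in the same direction inflates its apparent share. Section 8.3 intends these results to suggest which parts of the app or its implementation need strengthening, so a biased indirect effect could direct that work to the wrong place.

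**Working it through.** **The plan's own figures.** The documents give no figure for the mediation analysis. Section 8.2 supplies the setting: "40% retained in TAU vs 59.7% retained in reSET-O + TAU", two-sided 5%, 80% power, 100 per arm.

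- n per arm = [1.960·√(2·0.4985·0.5015) + 0.8416·√(0.40·0.60 + 0.597·0.403)]² / 0.197² = (1.386 + 0.583)² / 0.0388 ≈ 100. Power at 100 per arm is 80.03%.
- Odds ratio = (0.597/0.403)/(0.40/0.60) = 2.22, a log odds ratio of about 0.8.

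Both reproduce.

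**Size of the bias.** Let the app shift the mediator by *a* SD, let the baseline and follow-up scores correlate at *r*, and let the baseline score change the log-odds of retention by *g* per SD. Let the mediator itself have no effect. Within arm the follow-up score has variance 1 and covariance *r* with baseline. A retention model that omits baseline therefore gives the mediator a coefficient of about *r·g*, and the spurious indirect effect is about *a·r·g*. It is zero when *a* = 0.

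**How often the interval excludes zero.** Simulated trials had 200 patients, a linear mediator model, a logistic retention model and a Monte Carlo interval for the product. All values of *a*, *r* and *g* are assumptions, given as absolute sizes. Ranges cover repeated runs.

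| a | r | g | a·r·g | Simulated mean (log-odds) | As written | Baseline score added |
|---|---|---|---|---|---|---|
| 0 | – | – | 0 | – | 2-3.6% | – |
| 0.2 | 0.5 | 0.2 | 0.02 | – | 2.4% | – |
| 0.3 | 0.5 | 0.2 | 0.03 | 0.03 | 4.2% | – |
| 0.2 | 0.5 | 0.4 | 0.04 | – | 5.6% | – |
| 0.4 | 0.5 | 0.2 | 0.04 | – | 7.0% | – |
| 0.4 | 0.5 | 0.4 | 0.08 | 0.08 | 17.5-20% | about 4% |
| 0.4 | 0.6 | 0.6 | 0.14 | 0.14 | 48-51% | 3-4% |
| 0.5 | 0.7 | 0.8 | 0.28 | 0.26 | 86-90% | about 5% |

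A dash means not reported for that setting. The formula tracks the simulated means closely.

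**Second method.** This used a percentile bootstrap (500 resamples, 600 trials per setting) with a linear-probability retention model standing in for the planned SEM. Control retention was 40%, the direct log odds ratio 0.8, *r* 0.5 to 0.7, and the baseline odds ratio 1.5 to 2.0 per SD.

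| a | As written | Mean spurious effect (points of retention) | Baseline score added |
|---|---|---|---|
| 0 | 1.0-4.5% | about 0 | 0.0-0.3% |
| 0.3 | 16.7-47.7% | 1.5-3.2 | 2.7-3.5% |
| 0.5 | 24.8-84.3% | 2.2-5.4 | 4.2-6.7% |

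Hand check of the smallest non-zero case: 0.3 × 0.5 × ln 1.5 = 0.061 on the log-odds scale. Multiplied by p(1−p) ≈ 0.25, this is 1.5 points. With 600 trials the standard error at 5% is √(0.05·0.95/600) = 0.9 points, so 6.7% lies within two standard errors of the nominal level.

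**The case against.** The strongest reply is the general covariate rule in section 8.3. The sentence on the indirect effect defines a product estimator and is not a covariate list, and the plan speaks of testing mediation, so the rule could reach these models. A reader might infer that the plan forbids anything beyond treatment; the documents do not support that. But the rule selects on association in the trial data and does not name baseline mediator scores. The covariates that section 8.3 does name, the two stratification factors, are assigned to the primary and secondary analyses. The rule is a partial answer: adjustment is unspecified, not excluded.

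Second, a reader might infer that false mediation is automatic. It is not: with no app effect on the mediator, the interval excludes zero no more often than the nominal 5%.

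Third, the sizes rest on assumptions. The 90% end needs one baseline score to carry an odds ratio of exp(0.8) = 2.2 per SD, as large as the whole treatment effect in section 8.2. Under weaker values there is little or no excess of false positives, although the estimate is still biased. The clean result after adjustment follows from making the baseline score the only confounder. All of this stands.

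Fourth, section 8.3 claims only heuristic value and refers partly to main effects on the mediators, which randomisation protects. That limits the consequence but does not remove the bias from the indirect effect.

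**Conclusion.** The concern holds in a conditional form. The mediator-to-retention path is open to confounding by baseline status, and the plan does not specify the adjustment that would address it. For a mediator that the app shifts, the indirect effect can be biased by roughly *a·r·g* on the log-odds scale: 0.02 to 0.28 over the non-zero settings tried. With no true mediator effect, the interval excludes zero in about 2-7% of trials with a 0.2 SD shift or a baseline effect of 0.2 log-odds per SD. This rises to about 20-90% with shifts of 0.4-0.5 SD and baseline effects of 0.4-0.8. Adding the baseline score brings it to about 1-6%, if nothing else confounds.

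The mechanism is secure. The percentages are illustrative, because the documents give none of the three inputs and the simulations approximate the planned SEM.

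Two stronger readings should be avoided. The primary randomised comparison is not affected. Nor does the plan collect the baseline value of every mediator as listed: this is true of PROMIS but not of EuroQol. This is a worthwhile, low-cost improvement to an exploratory analysis.

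**What to change.** In section 8.3, extend the definition of the indirect effect so that, alongside treatment assignment, both the mediator equation and the retention equation include:

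- the baseline value of that mediator;
- the medication/site stratum;
- baseline intravenous drug use;
- baseline opioid-use days;
- probable major depression at baseline.

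Treatment must stay in the model. Simulated with the baseline mediator included but treatment left out of the retention equation (direct log odds ratio 0.8, no true mediator effect), the interval excluded zero in about 6-14% of trials over the three stronger settings.

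Add a sensitivity analysis for remaining mediator-outcome confounding, reporting how strong an unmeasured confounder would have to be to remove the indirect effect. Baseline adjustment deals only with what is measured.

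Name PROMIS as the social-functioning mediator in place of EuroQol in the section 8.3 list, or otherwise reconcile that list with the mediation paragraph and section 7.2.1.

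The cost is SAP wording and a few model terms. Once the social-functioning instrument is settled, no new data are needed. With one mediator at a time, the retention model has eight terms (treatment, mediator, baseline mediator, two for stratum, and three others). Under section 8.2 about 40 + 59.7 ≈ 100 patients are retained and 100 are not, or about 12 per term, which is workable.

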9.0 Data and Safety Monitoring Plan

9.1 Periodic evaluation of data

Data is directly entered into REDcap by the research assistants. The research coordinator will periodically check the data as it is entered to ensure REDcap is working properly and recording the data as appropriate. Regular quality assurance monitoring will be conducted by [name] (Columbia) who will remotely review regulatory documentation, data collection and data management procedures, and review other study documentation (e.g., progress notes, error corrections, contingency management logs). These reviews will also include: 100% review of informed consents, eligibility criteria, AE and SAE documentation, and protocol violations.

9.2 Data that are reviewed

Data reviews include regulatory documentation, data entered directly into REDcap, progress notes, error corrections, contingency management logs, informed consent and eligibility criteria, AE and SAE documentation, and protocol violations.

9.3 Method of collection of safety information

Study progress and safety will be reviewed weekly via conference call with the Study PIs and research team. Progress reports, including patient recruitment, retention/attrition, and AEs, will be provided to PIs following each of the QA monitoring visits. An Annual Report will be compiled and will include a list and summary of AEs. The Annual Report will be submitted to the data safety monitoring board (DSMB), IRB and NCCIH per their requirements. The IRB and other applicable recipients will review progress of this study on an annual basis.

9.4 Frequency of data collection

Data collection is ongoing as it includes cumulative data (data received from the reSET-O app) and discrete data (data collected by surveys as completed at the research visits – baseline and week 4, 8, 12, and 24 visits).

9.5 Individuals reviewing the data

Oversight of data management, including data collection, storage, and export, security, tracking, data analysis software and hardware, and quality assurance will be the responsibility of Drs. [name] and [name]. A senior (bio)statistician and master's level analyst from the CTSI at Penn State College of Medicine will conduct analysis of REDCap survey data as well as app data from Pear Therapeutics. [name], senior Biostatistician at CUMC, will be available for consultation as needed throughout the data analysis process but will not play an active role in the analysis itself. [name], under supervision of Drs. [name] and [name], will be responsible for monitoring of data export, storage, and management. Weekly remote meetings will take place between Drs. [name] and [name], [name], and study site research staff.

9.6 Frequency of review of cumulative data

Cumulative data includes data collected by the app, reSET-O. Data checks will occur regularly including anytime a subject who has been assigned to reSET-O+TAU meets with a research coordinator for a research appointment or meets with their clinician involved in their substance abuse treatment and is affiliated with the PPI Hub and/or RASE or JFT. These clinicians are defined as reSET-O research study coordinators, PPI Hub counselors, PPI Hub physicians, PPI Hub nurse practitioners, JFT "Certified Recovery Specialist's" or RASE care coordinator. These clinicians will login to the clinician dashboard side of the app and view how many modules the client has completed and the amount of rewards the client has earned, as well as logging urine drug screens as favorable or unfavorable. If a subject reports problems with the app or a clinician notes problems with the app and how data may be recorded, Pear Therapeutics, Inc. will be notified immediately to mitigate the issue(s).

9.7 Statistical tests

Drs. [name] and [name] will provide oversight to the statistical analysis process, ensuring timely provision of cleaned and locked data to the statistics team; data will be shared with the CTSI statistician and analyst following data lock, and [name] (Columbia) will provide as needed consultation on data and statistical issues throughout the trial. Detailed statistical analysis plan is described under Section 8.3, above

9.8 Suspension of research

This study will be stopped prior to its completion if: (1) the intervention is associated with adverse effects that call into question the safety of the intervention; (2) difficulty in study recruitment or retention will significantly impact the ability to evaluate the study endpoints; (3) any new information becomes available during the trial that necessitates stopping the trial; or (4) other situations occur that might warrant stopping the trial.

10.0 Risks

In general, risks associated with research comprised of behavioral interventions are low. reSET-O is a behavioral intervention that provides education about skills for avoiding drug use and otherwise improving health, modest incentives for adherence to treatment, and enhanced communication with providers, features which entail little anticipated risk. Potential risks for the research participation include psychological discomfort, answering sensitive questions related to substance use, mental health, and sexual behaviors, loss of confidentiality, and disclosure of information that meets reporting requirements. The interventions (reSET-O + TAU; TAU alone) may be ineffective, and patients' opioid use or associated problems may get worse.

There is a risk of loss of confidentiality as absolute confidentiality cannot be guaranteed. However, research staff will take precautions and maintain data created by participants to the degree permitted by the technology used in order to attempt to prevent loss of confidentiality.

There is a risk of randomization as only half of the participant population will receive reSET-O + TAU (n=100). Therefore, subjects who are assigned to TAU alone will not be exposed to the content affiliated with the reSET-O

app, including psychoeducation about skills for avoiding drug use and otherwise improving health. These subjects will also not receive the monetary incentives for adherence to treatment as affiliated with the app, or the monetary incentive to complete the qualitative interview as this interview is specific to the use of the reSET-O app.

All of the assessment surveys or questionnaires outline above may lead to some psychological discomfort as participants discuss sensitive areas related to high risk drug or sexual behaviors. They may feel uncomfortable answering such questions and/or become distressed when faced with reviewing their involvement in high risk behaviors.

Some of the questionnaires and interview questions will ask about participant feelings, such as depression, sadness, and anxiety. If responses indicate suicidal thoughts or risks of the subject hurting themselves or others, then we may need to break confidentiality and contact a licensed mental health professional or law enforcement officer. All subjects who express any suicidal thoughts will be referred for follow-up mental health counseling.

For subjects assigned to TAU + reSET-O, reSET-O should not induce any more discomfort than other treatments offered as part of outpatient substance abuse treatment. If participants become overly distressed, they will be directed to clinical staff working at their treatment program. Research staff (Research Coordinator and Research Assistants) will be trained in a safety protocol, so that if patients reveal acute distress or serious symptoms (e.g. depression or suicidal ideation) during a research assessment, the research staff will alert clinical staff at PACMAT, who will take over evaluating the situation and determine the severity of distress and if any additional evaluation or treatment is needed.

Subjects assigned to TAU + reSET-O will interact with reSET-O on the participant's mobile device (smartphone or tablet). A patient may interact with all the functionalities of reSET-O whether or not in the presence of a wireless signal or wifi. The program will update whenever coming in contact with wifi. Although information and answers within reSET-O cannot be accessed, the reSET-O website could become known and someone could look up the general website of the developer. They would be able to see that reSET-O (in general) and Pear Therapeutics, Inc. (the company that developed the reSET-O) are generally linked to substance abuse prevention and treatment.

Providers who are also considered subjects as a result of providing data about the app may be exposed to minimal risk. For instance, providers may find it cumbersome and time consuming to add some study related tasks to their overall workload; however, the goal of this study is not to add a significant amount of work to the providers; rather, the goal is to have the providers incorporate the use of the app during their clinical appointments with appropriate participants. We expect this workload to add approximately 6-12 minutes of additional time related to work tasks. Providers are free to engage in the app for longer than this if they plan to explore the app more and its resources. Providers may also find the open-ended discussion time consuming; however, they will only be asked to do this once.

The consent process will indicate the potential risks of participating in the study and participants will be advised that they do not have to answer questions with which they do not feel comfortable. The assessment will allow participants to skip any question they do not want to answer. The consent form will also indicate that participants are free to discontinue the study at any time for any reason with no explanation.

The summary of explanation of research for providers will outline any risks. It will be explained to providers that they are not required to participate in the open-ended discussion. They are not required to answer any questions about the app on the survey that they do not feel comfortable answering.

